7.1.4. Payment

Participants will be offered reasonable travel expense reimbursement for trial visits.

7.1.5. Randomisation

Those who provide informed consent and fulfil eligibility criteria will be randomly allocated stratified by psychosocial status (PHQ-4 score≥6 (Penlington et al., 2020)) and site in a ratio of 1:1:1 to one of the three arms of the study: TAU, lidocaine injections, or Botulinum toxin type A injections 3 monthly for 3 cycles (weeks 0, 12, 24). The randomisation process will use the Sealed Envelope (SE) system (a central, secure, 24-hour web-based randomisation system with concealed allocation). The SE system will use random permuted blocks within strata. Those who have been delegated the randomisation task at local sites will be provided with personal login IDs and passwords. The study is open label. Those participating in the trial north-east of England (Newcastle, Sunderland, Middlesbrough sites) will be offered the opportunity to participate in the optional MRI sub-study. Seventeen participants from each arm of the trial will be sequentially selected from those who opt-in to the sub-study making a total of 51 participants in the sub-study.

7.2. Blinding

As the treatments have differing modes of delivery and differing adverse effects that would identify them easily the trial is designed as an open label trial. As a result, therefore blinding of the participant, clinical team, Health Economics and the TMG is not possible.

The trial statisticians (senior statistician and trial statistician) will be unblinded to produce and review reports to the Independent Data Monitoring Committee (IDMC). Unblinded reports will be kept confidential and will only be viewed by the IDMC members and the trial statisticians. The statistical analysis plan will be written and approved by the trial statisticians prior to any access to unblinded outcome data. The statistical methodology lead will remain blinded to outcome data until data lock for the final analysis. Should any amendments to the statistical analysis plan be required after the

senior and trial statisticians have accessed unblinded outcome data these can be reviewed and approved by the blinded statistical methodology lead.

7.3. Out of hours contact

Due to the low risk and unblinded nature of the trial and the fact it involves commonly used medications with a substantial body of evidence for their safety, there will be no out of hours contact for the central trial team. At each secondary care site participants will be able to access the usual NHS out-of-hours system for that site for any clinical problems.

As this is an unblinded, open label trial participants will be able to inform any clinician managing them in a medical emergency of the treatment they have had. To further enhance safety, they will be issued with a trial information card with all the trial's details on including the treatments and the local team's in hours contact details for quick and easy reference. They will be advised to always carry this on their person. Local sites' on call arrangements for any urgent problems with a trial participant will apply.

Any out of hours contacts will be recorded, via the HUQ or, if related to an adverse effect, through routine study visit procedures.

7.4. Trial Assessments

After written informed consent is given, a variety of assessments will be used to capture the data required from participants as they progress through the trial.

7.4.1. Pregnancy test

Where indicated a urine dip stick test will be carried out at visit 1 (Face-to-face screening visit). This will be conducted prior to any other assessments. If positive the patient will be a screen failure and no further data will be collected. If the chronology allows, the patient may be rescreened post-partum if they are not breastfeeding the child.

7.4.2. Visit 1 – Face to face screening visit (day -28 up to -1)

Following informed consent, a negative pregnancy test, and confirmation of eligibility, data will be captured at visit 1 (screening) prior to randomisation within the clinical data management system (CDMS), including the following:

- Sex at birth
- Age
- Ethnicity
- Home postcode to calculate index of multiple deprivation
- Current employment details, or reason for not working.
- Income, or details of benefits received.
- Highest level of education

- Relevant past medical history including: systems enquiry; allergies; current treatment and medications; any non-drug therapies; analgesia use in the last month and reason.
- TMD history including: duration of M-TMD to nearest month; other (known) TMD diagnoses; TMD treatment history and dates of treatment to nearest month.
- Migraine history using ID Migraine to screen. A positive screen will result in collection of details on: number of headache days per month categorised into <10days, 10-15 days, >15 days, any accompanying symptoms to the headache, and a MIDAS questionnaire.

The CRF will also capture the diagnoses elicited from the clinical review and examination derived from the Diagnostic Criteria for TMD (Schiffman et al., 2014). A routine extra and intra-oral examination will be conducted examining: cranial nerves V and VII, temporomandibular joint including pain-free opening and maximum unassisted opening, masseter and temporalis, cervical lymph nodes, salivary glands, screening of intra-oral soft and hard tissues to note any gross and relevant mimicking or serious pathology and not including periodontal examination. Vital signs will be recorded including weight, height, blood pressure, and pulse.

Research assessments as detailed in the schedule of events will be conducted prior to randomisation following confirmation of eligibility.

Eligible participants will be randomised at the end of the screening visit (visit 1). A follow up visit (visit 2) will be scheduled following randomisation to start treatment for those participants randomised to Botox or lidocaine. This should ideally be within 14 days of screening but may be up to 28 days. Administration of IMP may occur on the same date as the screening visit, following randomisation, should the participant and investigator both agree to this.

For participants randomised to TAU, they may receive a prescription to obtain their medication at the screening visit, or their GP will be contacted to ask them to prescribe it. For those participants who agree to undergo an MRI, the participant should be advised not to start their medication until after the completion of the MRI, if possible.

7.4.3. Visit 2 – Day 0

Participants will commence treatment at visit 2. For those randomised to receive an injectable, this will be their first cycle of treatment. For those participants allocated to TAU, this will be the start date of their medication, but does not need to be an in-person visit. The start date of the medication will be reported on ePro by the participant or reported to the trial team by telephone who will record this date in the eCRF. Further visit dates will be calculated from this Day 0 timepoint.

7.4.4. Further visits (3, 4, and 5)

All participants will have completed the research assessments ahead of the follow-up visit as described in 7.4.6 and if not, further copies will be issued for completion prior to commencing the follow-up visit. Consent will be reconfirmed at each follow-up visit. Follow up and or further treatment will occur at visits 3 (week 12 + - 7 days), 4 (week 24 + - 7 days) and 5 (week 36 + - 7 days).

Follow up visit 3 at week 12 (+/- 7 days), visit 4 at week 24 (+/- 7 days) and follow up visit 5 at week 36 (+/- 7 days), will be conducted in person for all treatment arms. A clinical assessment will take place here, as well as a vital signs assessment. Participants allocated to Botox or Lidocaine will also receive their next cycle of injections at visits 3 and 4. Participants allocated to TAU will have their medication reviewed by the trial investigator and changes made, if required, at visits 3 and 4. Their GP will be written to, if necessary, to ask them to alter their prescription, based on the decision of the trial investigator. Treatment may also be provided by the site pharmacy, depending on local processes.

At the 36 weeks, patients will be returned to the care of their GP as per usual standard of care practice. The GP will discuss and agree with the patient how their care will be conducted after the trial. The research team will contact the patient by telephone 7 days after the 36 week visit to identify any adverse events in that time period. Two attempts will be made to contact the participant.

Case report forms will be completed as required at each trial visit to capture any changes in the medical history, migraine history (if relevant), and if receiving injectable therapy examination status of any facial nerve weakness using the House-Brackmann regional and global scores (Reitzen et al., 2009).

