7.4.5. Facial Weakness visit

If participants perceive any facial weakness in between scheduled visits, they will be able to contact their local team to arrange an ad hoc visit. During this visit they will be clinically reviewed either face-to-face or by videoconference using the House-Brackmann regional and global scores (Reitzen et al., 2009). They will also be asked to complete the FaCE scale to capture any effects of the weakness on their everyday lives (Kahn et al., 2001).

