7.4.6.10. Facial Clinimetric Evaluation (FaCE) scale

This is a validated 15-item instrument examining 6 domains related to facial nerve paralysis: facial movement, facial comfort, oral function, eye comfort, lacrimal control, social function (Kahn et al., 2001). It employs a five-point response scale: strongly agree (1) through don't know (3) to strongly disagree (5). Its total score ranges from 0 (most affected) to 100 (not affected) and is calculated by an algorithm. The scale will only be used if patients opt into its use due to their perception of a facial weakness after an injectable therapy has been applied.

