7.4.10. Schedule of Events

		Day -28 to -1ª (Visit 1)	Day 0 (Visit 2)	Week 12 (Visit 3) +/- 7 days	Week 24 (Visit 4) +/- 7 days	Week 36 (Visit 5) ^c +/- 7 days	Week 37 (+3 days)	Unscheduled Visit - Facial Weakness, medication concern, or other
Activity	Identification potential participants	Face-to-face screening	1 st dose of IMP ^a	Research Assessment IMP review and/ or provision ^b	Research Assessment IMP review and/ or provision ^b	Research Assessment	Phone call	Research Assessment (As/If required)
	Potential participant identification							
Clinical team providing care review clinical notes or databases	х							
Self-referring individual self- screens and makes email contact ¹	х							
Provide PIS +/- invitation letter/email as appropriate	Х							
	Consent & eligibility							
Informed Consent		х		X ^d	X ^d	x ^d		
Dipstick pregnancy Test		х				x ^e		
Confirmation of eligibility		x						
	Routine Data Collection ²							
Sociodemographics		x						
PMH (systems, meds, allergies, daily analgesia use, non-drug therapies)		х						
Medical review (systems, con meds, allergies, daily analgesia use, non-drug therapies)				х	х	х		
Clinical examination inc CN V & VII		X		х	x	х		
Blood pressure, Pulse, Weight, & Height. Height only at day screening		х		х	х	х		
Diagnosis & TMD history		Х						
ID-Migraine +/- Migraine history & MIDAS ²		x		x ^f	x ^f	χ ^f		
	Research assessments (occur prior to		tration or review of					
Pain reporting assessment & feedback		х		Х				

		Day -28 to -1 ^a (Visit 1)	Day 0 (Visit 2)	Week 12 (Visit 3) +/- 7 days	Week 24 (Visit 4) +/- 7 days	Week 36 (Visit 5) c +/- 7 days	Week 37 (+3 days)	Unscheduled Visit - Facial Weakness, medication concern, or other
Activity	Identification potential participants	Face-to-face screening	1 st dose of IMP ^a	Research Assessment IMP review and/ or provision ^b	Research Assessment IMP review and/ or provision ^b	Research Assessment	Phone call	Research Assessment (As/If required)
PHQ-4 & red flag assessment		x		х	Х	х		
GCPS		х						
CPI (within GCPS ³)		x		х	х	Х		
OHIP-TMDs		x		х	х	Х		
EQ-5D-5L		х		х	х	Х		
BPSQI		х		х	х	Х		
SF-JFLS		х		х	х	Х		
GIC				х	х	Х		
LAEP				х	х	Х		
FaCE scale and facial				Optio	onal, as determined by	patient		х
weakness exam								
AE & SAE Reporting		х	х	х	х	Х	x ^g	х
HUQ		х		х		Х		
T&TQ					х			
MRI sub-study assessments: MRI & bone biomarkers ⁴		x (prior to IMP – TAU IMP may be started prior to MRI if it is not possible to delay)				x		

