9.3. Pre-specified AEs

As part of the trial, a number of adverse events of interest relating to Botox and Amitriptyline and Gabapentin will be collected as part of routine data collection. The events below are the pre-specified adverse events of interest and will therefore be collected:

- New onset headache
- Facial weakness following Botox (see section 7.4.5 for assessment/recording details).
- Other adverse effects listed within the Liverpool adverse events profile.

All adverse events that are considered as possibly related to any of the trial IMPs must be reported for the trial on the Adverse Event CRF.

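### Facial weakness: 7.4.4 records House-Brackmann in both injectable arms, but the schedule makes the examination optional and 9.3 names Botox only, so graded severity is open to differential ascertainment

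*Protocol*

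**What the plan says.** Section 7.4.4 describes the case report form content at visits 3, 4 and 5. It includes, "if receiving injectable therapy examination status of any facial nerve weakness using the House-Brackmann regional and global scores". No opt-in is mentioned, and both injectable arms are covered. The visits "will be conducted in person for all treatment arms".

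The schedule in 7.4.10 treats the examination differently. The row beginning "FaCE scale and facial" joins the FaCE questionnaire and the weakness examination. Its entry for the follow-up visits makes both optional at the patient's discretion (the cell text is broken in the available copy; the legible middle part is "onal, as determined by"). The row has a cross only under the unscheduled visit. A separate row, "Clinical examination inc CN V & VII", is crossed at screening and at weeks 12, 24 and 36 without restriction by arm.

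Section 9.3 lists as a pre-specified event "Facial weakness following Botox (see section 7.4.5 for assessment/recording details". Section 7.4.5, to which it refers, is the ad hoc visit: "If participants perceive any facial weakness in between scheduled visits, they will be able to contact their local team". Section 7.4.6.10 makes the FaCE scale available "if patients opt into its use due to their perception of a facial weakness after an injectable therapy has been applied".

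**The concern.** A site cannot follow 7.4.4 and the schedule together: one has House-Brackmann status captured at each follow-up visit in the injectable arms, and the other leaves the examination to the patient. Section 9.3 adds an asymmetry by naming one injectable, although 8.4 gives lidocaine at the same sites and in the same volumes.

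Comparing adverse effect profiles is a secondary objective (3.2 f), and participants and clinicians know the allocation (7.2). If grading depends on who perceives weakness and asks, and the protocol directs attention to one of the two injections, the graded severity in the two arms may differ for reasons unrelated to the drugs. Grades that were never recorded cannot be recovered at analysis.

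**Working it through.** No figure in the protocol is in dispute, so the check is a comparison of the places that govern facial weakness.

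| Place | What is captured | In whom | What triggers it |
|---|---|---|---|
| 7.4.4 | House-Brackmann status | Botox and lidocaine | Visits 3, 4, 5 |
| 7.4.10, combined row | FaCE and weakness examination | No arm stated | Patient's choice at follow-up visits; crossed at the unscheduled visit |
| 7.4.10, clinical examination row | Cranial nerves V and VII, no grade named | All arms | Screening, weeks 12, 24, 36 |
| 7.4.5 | House-Brackmann and FaCE | Any participant | Participant contacts the site |
| 7.4.6.10 | FaCE | After an injectable | Patient opts in |
| 9.3, list of events | Facial weakness as event of interest | Botox | Refers to 7.4.5 |
| 9.2, and last sentence of 9.3 | All adverse events, with severity; those possibly related to any trial drug | All arms | Occurrence |

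**Step 1: detection or grade.** The clinical examination row and 9.2 do not depend on opt-in, so weakness seen at a scheduled visit is recordable in any arm. The severity recorded under 9.2 is the general five-level scale of 9.1.1, not a House-Brackmann grade. The schedule attaches no grade to the cranial nerve examination. The exposed quantities are therefore the House-Brackmann grade, if the schedule is followed, and the FaCE score, which is opt-in by design.

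**Step 2: how many grades are at issue.** The arm size follows from section 10.3: (1 − 0.6²) × 251 = 160.6, so 161 per arm; 161 / 0.73 = 220.5, so 221 per arm; 3 × 221 = 663, which agrees with the protocol. Under 7.4.4, two injectable arms with three follow-up visits give at most 2 × 221 × 3 = 1,326 scheduled House-Brackmann records. If the planned 27% attrition all occurred before week 12, the number would be 2 × 161 × 3 = 966. Under the schedule's combined row, the number is whatever participants choose.

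**Step 3: mechanism.** Take two injectable arms of equal size n with the same true proportion p weak at a scheduled visit. Let a and b be the fractions of those affected who are graded after Botox and after lidocaine. Expected graded cases are n·p·a and n·p·b, so their ratio is a/b whatever the value of p. Under 7.4.4, a = b = 1 among those attending, and the ratio is 1. Under the schedule, a and b are set by perception and choice, and nothing makes them equal. The documents give no value for p, a or b.

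**Step 4: timing.** Injections are given at day 0, week 12 and week 24, and the scheduled examinations fall at weeks 12, 24 and 36, about 12 weeks after each injection. Weakness that appears and resolves in between is graded only if the participant asks for the visit in 7.4.5. Reconciling the schedule with 7.4.4 does not change that.

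**The case against.** The strongest reply is that weakness will be found anyway. The cranial nerve VII examination is scheduled in all arms, follow-up is in person, every adverse event is recorded with severity and causality, anything possibly related to lidocaine must be reported, and the ad hoc visit is open to everyone. This stands, and it limits the point to graded severity.

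A reader might infer that facial weakness rates depend wholly on volunteers and cannot be compared fairly between arms. The documents do not support that, for the reasons just given, and 7.4.4 itself treats the two injectables alike. Nor does any passage say that Botox participants are questioned differently from lidocaine participants. Assumed opt-in percentages could be made to show a spurious difference, but the protocol supplies none, so such figures would show only what was assumed.

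It can also be said that 7.4.4 speaks of any weakness and might mean grading only when weakness is present, that 9.3 is a list of events and not an examination rule, and that the word optional fits the FaCE half of the row. Each reading is possible and narrows the conflict. None explains why the weakness examination shares the optional entry, or why 9.3 omits lidocaine when 7.4.4 and 7.4.6.10 refer to injectable therapy in general. The case report form is not shown and could settle the matter in practice, but the protocol text would still conflict.

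Grading the usual-treatment arm as well would be a preference: those participants receive no facial injection, and 7.4.4 does not ask for it.

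**Conclusion.** The point holds as an inconsistency in data capture for a safety outcome. Sections 7.4.4, 7.4.10 and 9.3 do not agree on whether House-Brackmann grading is routine or at the patient's choice, or on whether facial weakness is an event of interest after both injectables. Detection is partly protected. Graded severity is open to differential ascertainment between Botox and lidocaine if sites work from the schedule and 9.3; if they work from 7.4.4, that problem does not arise at scheduled visits.

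The amount of distortion cannot be estimated from the protocol. What can be stated is the contrast in Step 2: a planned set of between 966 and 1,326 scheduled grades, given the protocol's own attrition figure and no other losses, against a self-selected number. The co-primary outcomes are not affected. The conclusion assumes that the combined row's entry covers the follow-up visits, as its position in the broken table indicates.

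**What to change.** Reconcile the three places.

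- **Schedule (7.4.10):** split the combined row. Keep the FaCE questionnaire optional. Show House-Brackmann as recorded at weeks 12, 24 and 36 in both injectable arms, taken from the cranial nerve VII examination already done.
- **Section 9.3:** define the event as facial weakness following either injectable, and refer to 7.4.4 as well as 7.4.5.
- **Reporting:** give, by arm, the number with an abnormal grade over the number examined. Show scheduled and ad hoc visits separately, because ad hoc findings still depend on participants asking for a visit.

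The cost is two wording changes and a short extra case report form entry per visit, from an examination that is already scheduled. No treatment, dose or stopping rule is altered.

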7.4.5. Facial Weakness visit

If participants perceive any facial weakness in between scheduled visits, they will be able to contact their local team to arrange an ad hoc visit. During this visit they will be clinically reviewed either face-to-face or by videoconference using the House-Brackmann regional and global scores (Reitzen et al., 2009). They will also be asked to complete the FaCE scale to capture any effects of the weakness on their everyday lives (Kahn et al., 2001).

7.4.6. Research assessments using self-report symptom-based questionnaires

The questionnaire administration schedule is detailed in the schedule of events (section 7.4.10, 'research assessments' in table). Administration will be electronic with links sent to participants via Sealed Envelope. Paper based questionnaires will be available for any participants with computer ability/access issues or for people who haven't completed by the time of their follow-up visit. Postage paid envelopes will be provided for return of questionnaires for those who lack computer access or competence. A verbal data completion option by telephone will also be possible if required.

7.4.6.1. Patient health questionnaire-4 (PHQ-4)

The PHQ-4 is a validated 4-item self-report instrument used to screen for psychosocial distress. It contains two items on depression and two on anxiety and is in widespread use in both primary and secondary care in the NHS. The instrument's minimum additive score is 0 and maximum is 12. Scores ≥9 indicate a substantial level of psychosocial distress and will be highlighted to both the patient and their GP for further investigation and management as appropriate alongside continuing in the trial unless there are concerns over patient safety (Kroenke et al., 2009).

7.4.6.2. Characteristic pain intensity (CPI) and Graded Chronic Pain Scale

The CPI is a validated three-item self-report instrument derived from the Graded Chronic Pain Scale examining current, average and worst pain intensity on a numerical rating scale of 0 (no pain) to 10 (worst pain imaginable) in the last three months. The instrument's total minimum score is 0 and maximum is 100 which are derived by taking the mean of the three responses and multiplying by 10.

The Graded Chronic Pain Scale will be used in full at screening and consists of 7 items. Three of the items are the CPI and the remaining four are related to disability experienced because of the persisting pain. Three of the disability items use the same numerical rating scale as the CPI and the other uses a four-choice categorical response. The GCPS produces five ordinal outcomes via an algorithm: I (lowest pain-related disability), IIa, IIb, III, IV (highest pain related disability).

